8.4 Dose modification and management of toxicities

All toxicities will be graded according to CTCAE version 4.0. Following the first dose of durvalumab and tremelimumab, subsequent administration of durvalumab and tremelimumab can be modified based on toxicities observed as described in [Sections 8.5, 8.6, and 8.7](#). For adverse events (AEs) that are considered at least partly due to administration of durvalumab or tremelimumab, the following general guidance may be applied:

- Treat each of the toxicities with maximum supportive care (including holding the study therapy suspected of causing the toxicity where required).
- All dose modifications should be documented with clear reasoning and documentation of the approach taken.
- In addition to the criteria for permanent discontinuation of study therapy based on toxicity grade, permanently discontinue study therapy for the conditions outlined in [Section 8.2.2](#).

Table 7. Treatment management for study therapy (durvalumab and tremelimumab)

CTCAE v4.0 Adverse Event	CTCAE v4.0 Grade	Action to be Taken with Study Therapy	
		Tremelimumab	Durvalumab
Cardiac Disorders			
Myocarditis (See Sections 8.5.1 and 8.5.12)	1	For suspected myocarditis: Hold study therapy until full diagnostic work up. Initiate steroid therapy and appropriate management. If study therapy is held, resume after complete resolution to Grade 0 after completion of the steroid taper, resume at the next scheduled dose.	
	2	Hold study therapy dose until resolution to Grade 0. If toxicity rapidly improves to Grade 0, then: The decision to reinstitute study therapy will be based upon treating physician’s clinical judgment and after completion of steroid taper. If toxicity does not rapidly improve, permanently: Discontinue study therapy.	
	3-4	Discontinue study therapy	
Endocrine disorders			
Endocrinopathy (e.g., hyperthyroidism, hypothyroidism, Type 1 diabetes mellitus, hypophysitis, hypopituitarism, and adrenal insufficiency; exocrine event of amylase/lipase increased also included in this section) (See Sections 8.5.1 and 8.5.8).	1	No dose modifications.	

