Platelet count decreased (See Section 8.5.11.)	2	Hold until \leq Grade 1 or baseline, then resume and: Maintain dose or \downarrow one dose level.	Hold until \leq Grade 1 or baseline, then resume and: Maintain dose
	3	Hold until \leq Grade 1 or baseline, then resume and: \downarrow one dose level.	Hold until \leq Grade 1 or baseline, then resume and: Maintain dose
	4	Discontinue study therapy	
	Musculoskeletal and connective tissue disorders		
Myositis/Polymyositis (See section 8.5.13)	1	No dose modifications.	
	2	Hold study therapy dose until resolution to Grade ≤ 1 . Discontinue study therapy if it does not resolve to Grade ≤ 1 within 28 days or if there are signs of respiratory insufficiency.	
	3	Hold study therapy dose until resolution to Grade ≤ 1 . Discontinue study therapy if Grade 3 imAE does not resolve to Grade ≤ 1 within 28 days or if there are signs of respiratory insufficiency.	
	4	Discontinue study therapy	

Table 7 continued on next page.

Table 7. Treatment management for study therapy (continued)

CTCAE v4.0 Adverse Event	CTCAE v4.0 Grade	Action to be Taken with Study Therapy	
		Tremelimumab	Durvalumab
Nervous system disorders			
Neurotoxicity (to include but not be limited to limbic encephalitis and autonomic neuropathy, excluding Myasthenia Gravis and Guillain-Barre) (See Sections 8.5.1 and 8.5.9.)	1	Hold study therapy during neurotoxicity work-up. If diagnosis of Myasthenia Gravis or Guillain-Barre is confirmed, discontinue study therapy. Otherwise, maintain study dose level.	
	2,3	Hold study therapy during neurotoxicity work-up. Once elevations have resolved to \leq Grade 1, and if 
 no systemic steroid therapy has been initiated, then resume: \downarrow 1 dose level. systemic steroid therapy has been initiated –after completion of the steroid taper: resume \downarrow 1 dose level or discontinue If steroid taper completion is $>$ 28 days: discontinue further study therapy. 	
	4	Discontinue study therapy	
Peripheral neuromotor syndrome (such as Guillain-Barre and myasthenia gravis) (See Sections 8.5.1 and 8.5.10.)	1	No dose modifications.	
	2	Hold study therapy dose until resolution to Grade \leq 1. Permanently discontinue study therapy if it does not resolve to Grade \leq 1 within 28 days or if there are signs of respiratory insufficiency or autonomic instability.	

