	3	Hold study therapy dose until resolution to Grade \leq 1. Permanently discontinue study therapy if it does not resolve to Grade \leq 1 within 28 days or if there are signs of respiratory insufficiency or autonomic instability.	
	4	Discontinue study therapy	
Respiratory, thoracic, and mediastinal disorders			
Pneumonitis/pulmonary infiltrates/other pulmonary events 
 Dyspnea Hypoxia Pneumonitis ILD Pulmonary fibrosis (See Sections 8.5.1 , 8.5.3 , and 8.6.1.)	Hold study treatment until pneumonitis is evaluated.		
	1	Maintain study therapy schedule without delay.	
	2	Hold study therapy. At physician's discretion, once event is stabilized to \leq Grade 1 after completion of the steroid taper, then resume: \downarrow one dose level. If steroid taper completion is $>$ 28 days: discontinue further study therapy.	
3,4	Discontinue study therapy		

Table 7 continued on next page.

Table 7. Treatment management for study therapy (continued)

CTCAE v4.0 Adverse Event	CTCAE v4.0 Grade	Action to be Taken with Study Therapy	
		Tremelimumab	Durvalumab
Skin and subcutaneous tissue disorders			
Rash/dermatitis (e.g., acneiform, maculo-papular) (See Sections 8.5.1 and 8.5.7.)	1	Maintain dose level	
	2	Hold study therapy until resolution to ≤ Grade 1 or baseline and if 
 no systemic steroid therapy has been initiated—resume: Maintain dose level or ↓ one dose level. systemic steroid therapy has been initiated –after completion of the steroid taper: Maintain dose level or ↓ one dose level. If steroid taper completion is > 28 days: discontinue further study therapy .	
	3	Hold study therapy until resolution to ≤ Grade 1 or baseline and if 
 no systemic steroid therapy has been initiated—resume: ↓ one dose level or discontinue. systemic steroid therapy has been initiated –after completion of the steroid taper: ↓ one dose level or discontinue. If steroid taper completion is > 28 days: Discontinue further study therapy .	
	4	Discontinue study therapy	
Rash (e.g., bullous skin formations) (See Section 8.5.7)	All Grades	Discontinue study therapy	
AEs of Non-Immune Mediated Reactions			
AEs of non-immune mediated reaction requiring dose modification per investigator (e.g., Section 8.5.1)	1	Maintain dose	

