 - Promptly initiate empiric IV methylprednisolone 1 to 2 mg/kg/day or equivalent.
 - If no improvement within 3-5 days despite IV corticosteroids, consider additional workup and promptly treat with additional immunosuppressants (e.g. IVIG).
 - Once stable, gradually taper steroids (28 days of taper) and consider prophylactic antibiotics, antifungals and anti PJP treatment (refer to current NCCN guidelines for treatment of cancer-related infections [Category 2B recommendation]). Permanently discontinue study therapy if Grade 3 imAE does not resolve within 28 days.
- *Grade 4:*
 - Discontinue study therapy.
 - Report event to DSSM.
 - Obtain Neurology consultation.
 - Promptly initiate empiric IV methylprednisolone 1 to 2 mg/kg/day PO or equivalent.
 - If no improvement within 3-5 days despite IV corticosteroids, consider additional workup and promptly treat with additional immunosuppressants (e.g. IVIG).
 - Once stable, gradually taper steroids (28 days of taper) and consider prophylactic antibiotics, antifungals and anti PJP treatment (refer to current NCCN guidelines for treatment of cancer-related infections [Category 2B recommendation]).

8.5.10 **Peripheral neuromotor syndromes**
(Immune-mediated peripheral neuromotor syndromes such as Guillain-Barre and Myasthenia Gravis)

The prompt diagnosis of immune-mediated peripheral neuromotor syndromes is important, since certain patients may unpredictably experience acute decompensations which can result in substantial morbidity or in the worst case, death.

Patients should be monitored for signs and symptoms that may include peripheral sensory neuropathy, muscle weakness, peripheral neuropathy (including numbness, tingling, and sensitivity to touch). Special care should be taken for certain sentinel symptoms which may predict a more severe outcome, such as prominent dysphagia, rapidly progressive weakness, and signs of respiratory insufficiency or autonomic instability.

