Patients should be evaluated to rule out any alternative etiology (e.g., disease progression, infections, metabolic syndromes and medications, etc.). It should be noted that the diagnosis of immune-mediated peripheral neuromotor syndromes can be particularly challenging in patients with underlying cancer, due to the multiple potential confounding effects of cancer (and its treatments) throughout the neuraxis. Given the importance of prompt and accurate diagnosis, it is essential to have a low threshold to obtain a neurological consult. **If Myasthenia Gravis or Guillain-Barre is confirmed, discontinue study therapy.**

Neurophysiologic diagnostic testing (e.g., electromyogram and nerve conduction investigations, and “repetitive stimulation” if myasthenia is suspected) are routinely indicated upon suspicion of such conditions and may be best facilitated by means of a neurology consultation.

It is important to consider that the use of steroids as the primary treatment of Guillain-Barre is not typically considered effective. Patients requiring treatment should be started with IV IG and followed by plasmapheresis if not responsive to IV IG. See [Table 7](#).

- *Grade 1:*
 - Hold study therapy.
 - Contact DSSM.
 - Care should be taken to monitor patients for sentinel symptoms of a potential decompensation as described above.
 - Obtain a Neurology consult unless the symptoms are very minor and stable. If Myasthenia Gravis or Guillain-Barre is confirmed, discontinue study therapy and report event to DSSM.
- *Grades 2, 3 and 4:*
 - Hold study therapy during work-up of symptoms. If Myasthenia Gravis or Guillain-Barre is confirmed, discontinue study therapy. If negative hold therapy until \leq Grade 1 and prednisone dose is \leq 10 mg/day or the equivalent.
 - Report event to DSSM.
 - Care should be taken to monitor patients for sentinel symptoms of a potential decompensation as described above.
 - Obtain a Neurology consult.
 - Sensory neuropathy/neuropathic pain may be managed by appropriate medications (e.g., gabapentin, duloxetine, etc.).

MYASTHENIA GRAVIS

- Steroids may be successfully used to treat Myasthenia Gravis. Important to

consider that steroid therapy (especially with high doses) may result in transient worsening of myasthenia and should typically be administered in a monitored setting under supervision of a consulting neurologist.

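### For a Grade 1 peripheral neuromotor event, Table 7 makes no change to dosing while Section 8.5.10, which that row cites, orders a hold, and no sentence says which prevails

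*Combined protocol and SAP*

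**What the plan says.** Section 8.4, Table 7, has a row headed "Peripheral neuromotor syndrome (such as Guillain-Barre and myasthenia gravis) (See Sections 8.5.1 and 8.5.10". At Grade 1 the action for both drugs is "No dose modifications". At Grades 2 and 3 the row holds until the event is Grade 1 or lower, with permanent discontinuation if that takes more than 28 days or if there are signs of respiratory insufficiency or autonomic instability. At Grade 4 it discontinues.

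Section 8.5.10 covers the same syndromes. Its Grade 1 list starts with "Hold study therapy", then asks the site to contact the sponsor's study management department and to watch for sentinel symptoms. It continues with "Obtain a Neurology consult unless the symptoms are very minor and stable" and requires discontinuation if either diagnosis is confirmed. It does not say when a Grade 1 hold ends.

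A later 8.5.10 entry, written jointly for Grades 2, 3 and 4, describes how a hold is released when the work-up is negative. The separate Grade 4 entry that follows discontinues therapy, as Table 7 does.

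**The concern.** Table 7 is what a site is likely to have open when deciding whether to give an infusion. For the two diagnoses named in this row, its Grade 1 cell gives no reason to wait, although the section it cites says to wait. Section 8.5.10 explains why waiting may matter: "certain patients may unpredictably experience acute decompensations which can result in substantial morbidity or in the worst case, death". It adds that diagnosis is particularly difficult in patients with cancer, so a mild early presentation may not be settled quickly.

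Two sites seeing the same patient could act in opposite ways and each could cite the protocol. At stake is further checkpoint-inhibitor exposure while a potentially fatal immune toxicity is still being excluded. The efficacy analysis is not touched.

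**Working it through.** The question is one of text, so the check sets the instructions side by side and looks for a rule that reconciles them.

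**Step 1. Same event, same grade.**

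| Source | Grade 1 instruction | When a hold ends |
|---|---|---|
| Table 7, Peripheral neuromotor syndrome | "No dose modifications" | Not applicable |
| Section 8.5.10 | "Hold study therapy" | Not stated, unless the diagnosis is confirmed (then discontinue) |

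**Step 2. Could both be followed?** Only if the Table 7 entry means that the dose level stays the same and is silent on holding. The same column orders holds at Grades 2 and 3 of this row. The Neurotoxicity row just above writes out both parts at Grade 1: "Hold study therapy during neurotoxicity work-up. If diagnosis of Myasthenia Gravis or Guillain-Barre is confirmed, discontinue study therapy", followed by an instruction to keep the dose level. Where the table wants a hold at an unchanged dose, it says so. The two entries conflict.

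**Step 3. Is there a rule of precedence?**
- 8.1 bases decisions on the adverse event that needs the largest modification. That ranks events and does not choose between two instructions for one event.
- 8.2.2 discontinues on a diagnosis of Guillain-Barre or myasthenia gravis, whatever the grade. The gap lies before diagnosis.
- 8.3 places the toxicity instructions in Table 7. 8.5 refers dose management to Table 7 and calls its own guidelines recommended. The introduction to 8.5.10 also points to Table 7.
- 8.4 says that dosing after the first dose can be modified as described in 8.5, 8.6 and 8.7.

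The references run both ways, with more pointing to Table 7. No sentence says that one text overrides the other.

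**Step 4. Is the mismatch isolated?** Eleven Table 7 rows have their own Grade 1 entry and a matching 8.5 subsection: myocarditis, endocrinopathy, diarrhea/enterocolitis, infusion reaction, immune-mediated hepatitis, nephritis, myositis, neurotoxicity, peripheral neuromotor syndrome, pneumonitis and rash. An 8.5 order to hold at Grade 1 that Table 7 omits occurs in 1 of the 11, this row.

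**Step 5. What one event puts at stake.**
- Exposure: one Day 1 visit, with durvalumab 1500 mg and, in Cycles 2 to 4, tremelimumab 75 mg (Table 4). After Cycle 1 the schedule leaves 24 − 1 = 23 durvalumab and 4 − 1 = 3 tremelimumab doses. These are ceilings from the schedule, not expected numbers of errors.
- Time to decide: Table 2 places adverse event assessment within 72 hours (3 days) before Day 1, and 8.2 lets a dose move 3 days later. For an event first recorded at that visit, at most 3 days remain before the scheduled dose and 3 + 3 = 6 days before the window closes. If the work-up is still open on Day 1, Table 7 permits the infusion and 8.5.10 does not.

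**Step 6. Grade 4.** The joint entry for Grades 2, 3 and 4 in 8.5.10 describes release from a hold. Table 7 and the later 8.5.10 entry discontinue at Grade 4, so the release sentence cannot apply there.

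**The case against.** The best case on the other side is that the texts are not of equal rank. 8.3 and 8.5 send dosing to Table 7, 8.2.2 refers to Table 7 for further treatment requirements, and the 8.5 guidance is only recommended. Table 7 would then govern. That is a fair reading of where the references lean, but it does not help: the less protective instruction would control and the hold written in 8.5.10 would have no effect.

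A second argument is that an undiagnosed event belongs in the Neurotoxicity row, which holds during work-up and foresees that these diagnoses may be confirmed. This has some force, since neither Grade 1 neuromotor entry uses the word suspected. But that row's heading excludes both diagnoses, and a site that classifies the event under the row named for them finds no hold. The cross-reference to 8.5.10, the contact with the study management department and the weekly calls with investigators all lower the chance of a dosing error. They do not correct the cell.

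A reader might infer three stronger points that the documents do not support.
- That the row breaks a general Table 7 pattern of holding for suspected events. Myocarditis ("For suspected myocarditis: Hold study therapy until full diagnostic work up") and pneumonitis ("Hold study treatment until pneumonitis is evaluated") suggest this, but the Grade 1 cells for myositis and endocrinopathy match the disputed one, and the pneumonitis Grade 1 line itself keeps the schedule without delay.
- That the situation is likely to arise. The visit timing shows how it could arise, but no event rate is given.
- That the prednisone threshold of 10 mg/day in 8.5.10 conflicts with the completed taper required by 8.2.1. Both conditions can be met together, so that threshold needs no change.

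**Conclusion.** The inconsistency is real and can be confirmed from the text alone. At Grade 1, Table 7 and the section it cites give opposite instructions, and no sentence resolves them. The size is one infusion visit per event, given or withheld. The number of such events is unknown, and none is assumed here.

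The conclusion rests on two readings: that the Table 7 entry covers holds as well as dose level (Step 2), and that a site may classify an early event under the row named for these diagnoses. It does not depend on which text the sponsor meant to prevail. If Table 7, the hold in 8.5.10 is a dead letter; if 8.5.10, the cell is wrong.

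The Grade 4 overlap in 8.5.10 is a smaller drafting point. The hypotheses, the stage sizes of 12 and 21 and the threshold of 3 responses are unaffected. The correction should be made because it is nearly free and the toxicities concerned can be fatal.

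**What to change.** 1. **Table 7, Peripheral neuromotor syndrome, Grade 1.** Replace the entry with the rule already used at Grade 1 in the Neurotoxicity row, without the word neurotoxicity: hold both drugs during work-up, discontinue if either diagnosis is confirmed, otherwise maintain the dose level.
2. **Section 8.5.10, Grade 1.** Put the same hold-during-work-up and release wording here. Changing the table alone would leave 8.5.10 with an open-ended hold, and 8.2.2 requires discontinuation once a non-taper delay passes 28 days.
3. **Section 8.5.10, joint entry for Grades 2, 3 and 4.** Limit the release-from-hold sentence to Grades 2 and 3.

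Table 7 at Grades 2 and 3 needs no added sentence, because 8.2.2 already discontinues on a confirmed diagnosis.

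The cost is a wording amendment, with no extra data, visits or patients. The clinical downside is an occasional delayed dose for a Grade 1 event that proves benign; a work-up lasting beyond the 6 days in Step 5 would push that dose outside its window. If the sponsor prefers not to hold at Grade 1, that is a clinical decision, but 8.5.10 would then have to be changed to agree.

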8.5 Immune-mediated adverse events (imAEs)

Immune-mediated adverse events/imAEs are important risks of interest and include: pneumonitis/ interstitial lung disease (ILD), diarrhea/colitis, hepatitis and increases in transaminases, nephritis and increases in serum creatinine, dermatitis/rash and pruritus, endocrinopathy (hypo- and hyperthyroidism, adrenal insufficiency, hypophysitis/hypopituitarism and Type I diabetes mellitus), myocarditis, neuropathy/neuromuscular toxicity (such as myasthenia gravis and Guillain-Barre) and pancreatitis. In addition, infusion-related reactions and hypersensitivity/anaphylactic reactions with a different underlying pharmacologic etiology are also considered AESIs. See [Section 10.2](#).

Other inflammatory responses that are rare with a potential immune related etiology are also considered as AESIs and include but are not limited to pericarditis, sarcoidosis, uveitis, and other events involving the eye, skin, hematological and rheumatological events. It is possible that events with an inflammatory or immune mediated mechanism could occur in nearly all organs ([Durvalumab IB 2018](#)).

Thorough evaluation of these events should be performed to rule out any alternative etiology (e.g., disease progression, concomitant medications, or infections). In the absence of a clear alternative etiology, all events should be considered potentially immune related. For study treatment dose management related to imAEs, see [Table 7](#).

The following guidelines are *recommended* as management of the following immune-mediated reactions.

8.5.1 **Overall management for imAEs**

- Patients should be thoroughly evaluated to rule out any alternative etiology (e.g., disease progression, concomitant medications, infections, etc.).
- In the absence of a clear alternative etiology, all events should be considered potentially immune related.
- Symptomatic and topical therapy should be considered for low-grade (Grade 1 or 2, unless otherwise specified) events.
- For persistent (greater than 3 to 5 days) low-grade (Grade 2) or severe (Grade ≥ 3) events promptly start prednisone 1-2mg/kg/day PO or IV equivalent unless otherwise noted in subsequent sections.
- Some events with high likelihood for morbidity and/or mortality – e.g., myocarditis, or other similar events even if they are not currently noted in the guidelines – should progress rapidly to high dose IV corticosteroids (methylprednisolone at 2 to 4 mg/kg/day) even if the event is Grade 2, and if clinical suspicion is high and/or there has been clinical confirmation. Consider, as necessary, discussing with the study physician, and promptly pursue specialist consultation.
- If symptoms recur or worsen during corticosteroid tapering (28 days of taper), increase the corticosteroid dose (prednisone dose [e.g. up to 2-4 mg/kg/day PO or IV equivalent]) until stabilization or improvement of symptoms, then resume corticosteroid tapering at a slower rate (> 28 days of taper).
- More potent immunosuppressives such as TNF inhibitors (e.g. infliximab) should be considered for events not responding to systemic steroids. Progression to use of more potent immunosuppressives should proceed more rapidly in events with high likelihood for morbidity and/or mortality – e.g., myocarditis, or other similar events even if they are not currently noted in the guidelines – when these events are not responding to systemic steroids.
- With long-term steroid and other immunosuppressive use, consider need for *Pneumocystis jirovecii* pneumonia (PJP, formerly known as *Pneumocystis carinii* pneumonia) prophylaxis, gastrointestinal protection, and glucose monitoring.
- Discontinuation of study therapy is not mandated for Grade 3/Grade 4 inflammatory reactions attributed to local tumor response (e.g., inflammatory reaction at sites of metastatic disease and lymph nodes). Continuation of study therapy in this situation should be based upon a benefit-risk analysis for that patient.

Note: Non-imAEs should be treated as per institutional standard.

8.5.2 **Infusion reactions**

Management of reactions should be per institutional standard at the discretion of investigator. Monitor patients for signs and symptoms of infusion-related reactions

(e.g., fever and/or shaking chills, flushing and/or itching, alterations in heart rate and blood pressure, dyspnea or chest discomfort, skin rashes etc.) and anaphylaxis (e.g., generalized urticaria, angioedema, wheezing, hypotension, tachycardia, etc.). See [Section 8.5.1](#) and [Table 7](#).

The following are recommended management practices for infusion reactions:

- *Grade 1:*
 - The infusion rate of study therapy may be decreased by 50% or temporarily interrupted until resolution of the event.
 - Acetaminophen and/or antihistamines may be administered per institutional standard at the discretion of the investigator.
 - Consider premedication per institutional standard prior to subsequent doses.

Note: Steroids should not be used for routine premedication of < Grade 2 infusion reactions.

- *Grade 2:*
 - The infusion rate of study drug may be decreased 50% or temporarily interrupted until resolution of the event. Subsequent infusions may be given at 50% of the initial infusion rate.
 - Acetaminophen and/or antihistamines may be administered per institutional standard at the discretion of the investigator.
 - Consider premedication per institutional standard prior to subsequent doses.
 - Report event to DSSM.
- *Grade 3 and 4:*
 - Permanently discontinue study therapy.
 - Report event to DSSM.

Manage severe infusion-related reactions per institutional standards (e.g., IM epinephrine, followed by IV diphenhydramine and ranitidine, and IV glucocorticoid).

8.5.3 ***Pneumonitis/ILD***

Monitor patients for signs and symptoms of pneumonitis or interstitial lung disease (ILD) (e.g., new onset or worsening shortness of breath or cough). Patients should be evaluated with imaging and pulmonary function tests including other diagnostic procedures. Prompt treatment with steroids is important per guidelines below.

- Patients should be instructed to call the clinic to report any respiratory symptoms or changes they experience including:
 - cough
 - shortness of breath
 - dyspnea upon exertion
 - fever, and/or
 - chest pain.

For study treatment dose management related to imAEs, see [Section 8.5.1](#) and [Table 7](#).

- *Grade 1:*
 - Monitor and closely follow up in 2-4 days for clinical symptoms, pulse oximetry (resting and exertion) and laboratory work-up and then as clinically indicated.
 - Consider Pulmonary and Infectious Disease consult.
 - Consider holding study therapy as clinically appropriate and during diagnostic workup for other etiologies.

- *Grade 2:*
 - Hold study therapy until Grade 2 resolution to \leq Grade 1.
 - Monitor symptoms daily and consider hospitalization.
 - Promptly start systemic steroids (e.g., prednisone 1-2 mg/kg/day PO or IV equivalent).
 - Reimaging as clinically indicated.
 - If no improvement within 3-5 days, additional workup should be considered and prompt treatment with IV methylprednisolone 2-4mg/kg/day started.
 - If still no improvement within 3-5 days despite IV methylprednisolone at 2-4/g/kg/day, promptly start immunosuppressive therapy such as TNF inhibitors (e.g., infliximab at 5 mg/kg every 2 weeks). *Caution:* It is important to rule out sepsis and, if administered, refer to infliximab label for general guidance.
 - Once improving, gradually taper steroids (28 days of taper) and consider prophylactic antibiotics, antifungal or anti-pneumocystis pneumonia (PJP) treatment (refer to current NCCN guidelines for treatment of cancer-related infections [Category 2B recommendation]).
 - Consider Pulmonary and Infectious Disease consult.
 - Consider as necessary discussing with study physician.
 - Report event to DSSM.
- *Grade 3 or 4:*
 - Discontinue study therapy.
 - Promptly initiate empiric IV methylprednisolone 1 to 4 mg/kg/day or equivalent.
 - Obtain Pulmonary and Infectious Disease consult.
 - Hospitalize the patient.
 - Supportive Care (oxygen, etc.).
 - Report event to DSSM.
 - If no improvement within 3-5 days, additional workup should be considered and prompt treatment with additional immunosuppressive therapy such as TNF inhibitors started (e.g., infliximab at 5 mg/kg every 2 week dose). *Caution:* It is important to rule out sepsis and, if administered, refer to infliximab label for general guidance.
 - Once improving, gradually taper steroids over \geq 28 days and consider prophylactic antibiotics, antifungals and in particular, anti PJP treatment (refer to current NCCN guidelines for treatment of cancer-related infections [Category 2B recommendation]).

8.5.4 ***Diarrhea/enterocolitis***

Monitor for symptoms that may be related to diarrhea/enterocolitis (abdominal pain, cramping, or changes in bowel habits such as increased frequency over baseline or blood in stool) or related to bowel perforation (such as sepsis, peritoneal signs, and ileus).

Patients should be thoroughly evaluated to rule out any alternative etiology (e.g., disease progression, other medications, infections including testing for clostridium difficile toxin, etc.). Steroids should be considered in the absence of clear alternative etiology, even for low grade events, in order to prevent potential progression to higher grade event. Use analgesics carefully; they can mask symptoms of perforation and peritonitis. For study treatment dose management related to imAEs, see [Section 8.5.1](#) and [Table 7](#).

- *Grade 1:*
(*Diarrhea: stool frequency of <4 over baseline per day; Colitis: asymptomatic; clinical or diagnostic observations only*)
 - Close monitoring for worsening symptoms.
 - Consider symptomatic treatment including hydration, electrolyte replacement, dietary changes (e.g., American Dietetic Association colitis diet), and loperamide. Use of probiotics as per treating physician’s clinical judgment.
- *Grade 2:*
(*Diarrhea: stool frequency of 4 to 6 over baseline per day*) (*Colitis: abdominal pain; mucus or blood in stool*)
 - Hold study therapy until resolution to Grade ≤ 1 .
 - Consider symptomatic treatment including hydration, electrolyte replacement, dietary changes (e.g., American Dietetic Association colitis diet), and loperamide and/or budesonide.
 - Promptly start prednisone 1 to 2 mg/kg/day PO or IV equivalent.
 - If event is not responsive within 3-5 days or worsens despite prednisone at 1-2 mg/kg/day PO or IV equivalent, obtain GI consult for consideration of further workup such as imaging and/or colonoscopy to confirm colitis and rule out perforation, and prompt treatment with IV methylprednisolone 2-4 mg/kg/day started.
 - If still no improvement within 3-5 days despite 2-4mg/kg IV methylprednisolone, promptly start immunosuppressives such as (infliximab at 5mg/kg once every 2 weeks). Caution: Important to rule out bowel perforation and, if administered, refer to infliximab label for general guidance before using infliximab.
 - Once improving, gradually taper steroids (28 days of taper) and consider prophylactic antibiotics, antifungals and anti PJP treatment (refer to current NCCN guidelines for treatment of cancer-related infections [Category 2B recommendation]).
 - Report event to DSSM.
- *Grade 3 or 4:*
Grade 3 diarrhea: stool frequency of ≥ 7 over baseline per day; Grade 4 diarrhea: life threatening consequences. Grade 3 colitis: severe abdominal pain, change in bowel habits, medical intervention indicated, peritoneal signs; Grade 4 colitis: life-threatening consequences, urgent intervention indicated.
 - Permanently discontinue study therapy for Grade 3 if toxicity does not improve to Grade ≤ 1 within 14 days; study therapy can be resumed after completion of steroid taper.
 - Discontinue study therapy for Grade 4.
 - Promptly initiate empiric IV methylprednisolone 2 to 4 mg/kg/day or equivalent.
 - Monitor stool frequency and volume and maintain hydration.
 - Urgent GI consult and imaging and/or colonoscopy as appropriate.
 - Report event to DSSM.
 - If still no improvement within 3-5 days of IV methylprednisolone 2 to 4mg/kg/day or equivalent, promptly start further immunosuppressives (e.g. infliximab at 5 mg/kg once every 2 weeks).
 - Caution: Ensure GI consult to rule out bowel perforation and, if administered, refer to infliximab label for general guidance before using infliximab.
 - Once improving, gradually taper steroids (28 days of taper) and consider prophylactic antibiotics, antifungals and anti PJP treatment (refer to current

NCCN guidelines for treatment of cancer-related infections [Category 2B recommendation]).

8.5.5 **Hepatitis/hepatotoxicity**
(Elevation in AST, ALT, ALP and total bilirubin)

Monitor and evaluate liver function test: AST, ALT, ALP and total bilirubin (TB). Evaluate for alternative etiologies (e.g., viral hepatitis, disease progression, concomitant medications). **Infliximab should not be used for management of immune-related hepatitis.** Prompt treatment with steroids is important per guidelines below. For study treatment dose management related to imAEs, see [Section 8.5.1](#) and [Table 7](#).

- *Grade 1 AST or ALT and/or TB elevation:*
 - Continue LFT monitoring per protocol.
- *Grade 2 AST or ALT and/or TB elevation:*

Note: For patients with metastatic liver disease who enter the study with Grade 2 transaminases, maintain dose and continue study therapy without holding. Otherwise Hold study therapy.

 - Regular and frequent checking of LFTs (e.g. every 1-2 days) until elevations are improving or resolved.
 - If no resolution to \leq Grade 1 (*or baseline*) in 1-2 days, discuss with study physician. If event is persistent ($>$ 3-5 days) or worsens, promptly start prednisone 1-2 mg/kg/day PO or IV equivalent.
 - If still no improvement within 3-5 days despite prednisone 1-2mg/kg/day PO or IV equivalent, consider additional workup and prompt treatment with IV methylprednisolone 2-4 mg/kg/day started.
 - If still no improvement within 3-5 days despite 2-4 mg/kg/day of IV methylprednisolone, promptly start immunosuppressives (mycophenolate mofetil). Discuss with study physician if mycophenolate mofetil is not available.

Infliximab should NOT be used.

 - Once improving, gradually taper steroids (28 days of taper) and consider prophylactic antibiotics, antifungals and anti PJP treatment (refer to current NCCN guidelines for treatment of cancer-related infections [Category 2B recommendation]).
 - Report event to DSSM.

Grade 3 or 4 AST or ALT and/or TB elevation:

.For Grade 3:

- For elevations in transaminases $\leq 8 \times$ ULN, or elevations in bilirubin $\leq 5 \times$ ULN:
 - Hold study therapy dose until resolution to Grade ≤ 1 or baseline.
 - Resume study therapy if elevations downgrade to Grade ≤ 1 or baseline within 14 days and after completion of steroid taper.
 - Permanently discontinue study therapy if the elevations do not downgrade to Grade ≤ 1 or baseline within 14 days.
- For elevations in transaminases $> 8 \times$ ULN or elevations in bilirubin $> 5 \times$ ULN, discontinue study therapy.
- Permanently discontinue study therapy for any case meeting Hy's law criteria (AST and/or ALT $> 3 \times$ ULN + bilirubin $> 2 \times$ ULN without initial findings of cholestasis (i.e., elevated alkaline P04) and in the absence of any alternative cause.

Grade 4

- Discontinue study therapy.

Grade 3 or 4:

- Promptly initiate empiric IV methylprednisolone at 1 to 4 mg/kg/day or equivalent.
- If still no improvement within 3-5 days despite 1 to 4 mg/kg/day methylprednisolone IV or equivalent, promptly start treatment with immunosuppressive therapy (mycophenolate mofetil). Discuss with study physician if mycophenolate mofetil is not available.

Infliximab should NOT be used.

- Obtain a Hepatology consult, abdominal workup, and imaging as appropriate.
- Once improving, gradually taper steroids (28 days of taper) and consider prophylactic antibiotics, antifungals and anti PJP treatment (refer to current NCCN guidelines for treatment of cancer-related infections [Category 2B recommendation]).
- Report event to DSSM.

8.5.6 **Nephritis**

(serum creatinine elevation)

Obtain a Nephrology consult. Monitor for signs and symptoms that may be related to changes in renal function (e.g. routine urinalysis, elevated serum BUN and creatinine, decreased creatinine clearance, electrolyte imbalance, decrease in urine output, proteinuria, etc.). Patients should be thoroughly evaluated to rule out any alternative etiology (e.g., disease progression, infections etc.). Prompt treatment with steroids is important and should be considered in the absence of clear alternative etiology even for low grade events (Grade 2), in order to prevent potential progression to higher grade event. For study treatment dose management related to imAEs, see [Section 8.5.1](#) and [Table 7](#).

• *Grade 1:*

- Monitor serum creatinine weekly and any accompanying symptom.
- If creatinine returns to baseline, resume its regular monitoring per study protocol.
- Consider symptomatic treatment including hydration, electrolyte replacement, diuretics, etc.

• *Grade 2:*

- Hold study therapy until resolution to Grade ≤ 1 or baseline.
- Consider symptomatic treatment including hydration, electrolyte replacement, diuretics, etc.
- Carefully monitor serum creatinine every 2-3 days and as clinically warranted.
- Consult Nephrology and consider renal biopsy if clinically indicated.
- If event is persistent (> 3-5 days) or worsens, promptly start prednisone 1 to 2 mg/kg/day PO or IV equivalent.
- If event is not responsive within 3-5 days or worsens despite prednisone at 1-2 mg/kg/day PO or IV equivalent, additional workup should be considered and prompt treatment with IV methylprednisolone at 2-4 mg/kg/day started.
- Once improving gradually taper steroids (28 days of taper) and consider prophylactic antibiotics, antifungals and anti PJP treatment (refer to current NCCN guidelines for treatment of cancer-related infections [Category 2B recommendation]).

- When event returns to baseline, resume durvalumab (and tremelimumab if applicable) at the next scheduled study dose and routine serum creatinine monitoring per study protocol (see [Table 2](#)).
- Report event to DSSM.
- *Grade 3 or 4:*
 - Discontinue study therapy.
 - Carefully monitor serum creatinine on daily basis.
 - Consult Nephrology and consider renal biopsy if clinically indicated.
 - Promptly start prednisone 1 to 2 mg/kg/day PO or IV equivalent.
